Cover page

A randomized-controlled trial of therapy for children and adolescents with anxiety disorders and OCD

Downloaded from IRB website on 3/8/2023 Most recent approval: 9/20/2022

1. Project Title:

A randomized-controlled trial of therapy for children and adolescents with anxiety disorders and OCD

2. Investigator(s):

[name]. *Principal Investigator*

[name]. [name], M.A. [name], M.A. [name]. [name]. [name], M.A. *Co-Investigators*

[name] Study Coordinator

3. Abstract:

Anxiety disorders are among the most common psychiatric disorders in children and typically produce significant disruption in family, social, and academic functioning (Kathleen Rise Merikangas & Avenevoli, 2002). Fortunately, cognitive behavioral therapy (CBT) for childhood anxiety has been manualized and found to be efficacious (Walkup et al., 2008). CBT most often incorporate aspects of cognitive-restructuring, relaxation training, and exposure to anxietyproducing stimuli. Although research suggests that exposure is the most effective treatment component (S. P. H. Whiteside et al., 2020), many practitioners opt to utilize mainly cognitive and relaxation techniques at the expense of exposure techniques (S. P. H. Whiteside, B. J. Deacon, K. Benito, & E. Stewart, 2016). Parent-coached exposure therapy (PCET) is a treatment designed to maximize efficacy by highlighting exposure and has preliminary support (S. P. H. Whiteside et al., 2015). The current study aims to provide a more definitive test of the efficacy of PCET through a larger randomized controlled trial. In addition, the study will examine the effectiveness of individual as well as intensive group PCET. Finally, exploratory analyses will examine the effect of delivering treatment via video visits versus in person therapy. Sixty children and adolescents seeking treatment for anxiety in an outpatient pediatric anxiety clinic will be randomized to receive either individual PCET, individual traditional CBT, or the 5day intensive group PCET. The representativeness of the sample will be examined through a chart review of data collected in a clinical database (IRB# 611-05) of patients that accept and those that decline participation in the treatment study. Data regarding symptoms and impairment will be gathered from child- and parent-report, as well as clinical evaluators at the initial consultation,

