Participants. A total of 120 families (240 participants) (40 in each treatment condition) children and adolescents (aged 7 - 18 years) along with their parents will participate in the current study. The PADC typically evaluates more than 350 patients per year, approximately one-third of which continue into the treatment program. Thus, we anticipate a recruitment period of approximately twelve months in order to reach our goal of enrolling 240 participants in the study. To determine the degree to which the current study sample reflects the population of patients seen in the PADC, the clinical assessment data will be compared to patients not enrolled in the study, but for whom Research Authorization is available.

To be included, participants must a) be age 7 to 17, or 18 if still in high school and living at home; b) have a DSM-5 anxiety disorder diagnosis, including generalized anxiety disorder, obsessive compulsive disorder, panic disorder, agoraphobia, separation anxiety disorder, social and specific phobias, as assessed on the relevant modules of the (MINI-Kids; (Sheehan et al., 2010) by study staff in the PADC, c) be appropriate for the PADC standard weekly outpatient therapy program, d) be interested in starting outpatient therapy, e) have the anxiety disorder as their primary diagnosis, f) if taking a selective serotonin reuptake inhibitor, SNRI, tricyclic, or antipsychotic medication, agree to no changes during the 14 weeks of the study (medication status will be recorded from interview and using review of the electronic medical record).

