Patients will be excluded from the study if they meet any of the following criteria: (a) history of and/or current psychosis, autism, bipolar disorder, or current suicidality, or eating disorder as assessed during the initial clinical interview and all available clinical information; (b) current positive diagnosis in the child's caregiver of mental retardation, psychosis, or other psychiatric disorders or conditions that would limit his/her ability to understand CBT and follow-through with treatment directives (based on clinical interview); (c) secondary diagnosis of oppositional defiant disorder or major depression of sufficient severity to prevent anxiety treatment, (d) severity of symptoms that warrant higher level of care (i.e. intensive, residential, IOP, inpatient), (e) family is unable to attend weekly sessions (i.e. geographical or scheduling barriers), of (f) history of good quality exposure or CBT.

Procedures

See Figure 1. Participants who have contacted or been referred to the PADC for evaluation and treatment of an anxiety disorder will complete the standard clinical intake procedure for the PADC. Families whose children meet the inclusion criteria will be provided a description of the study procedures and asked which aspects of the study they are willing to participate in. All families will be asked to complete three research assessments (pre-, mid-, and post-treatment) consisting of completing questionnaires and a short phone or video call. Families will be provided with a description of the three treatment options and informed that PCET is the default treatment option. They will then be asked if they are willing to be randomized to a treatment from two or three of the options. Randomization will be accomplished through a random number generator and will allow for a comparison of the relative effectiveness of each treatment by

controlling for other variables that might impact treatment outcome. The individual PCET is currently the standard treatment offered through the PADC and patients not interested in this treatment are not eligible for the study. When families are interested and eligible in participating in the clinical trial, the therapist or a study coordinator will obtain written consent and assent.

Families who decline to participate will have the PADC.

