Following the consent process, families who agreed to be randomized to a comparison treatment participate will be assigned to a treatment condition through random assignment. Families that did not agree to randomization will be scheduled in PCET (individual or intensive group depending on preference). The families will then be scheduled to begin therapy at the earliest date available. All enrolled families will complete the pre-treatment research assessment the day they begin treatment. The families will then begin treatment.

The mid-treatment evaluation will be completed after the sixth session for patients in the individual treatment conditions and six weeks after the start of treatment in the intensive group condition. After the mid-treatment assessment families in all conditions can receive any type of therapy interventions with their study therapist. The final assessment will be completed 14 weeks after the first session. All study assessments and individual treatment sessions will be recorded, unless participants opt-out of recording, to examine therapist fidelity. Families will record progress each week using a study form which will be gathered by therapists during visits and by therapists (or other study staff) via electronic message or telephone calls in the absence of inperson appointments.

Tests/Measures Administered

Table 2 Summarizes when study measures are completed, by whom and whether they are administered as part of clinical practice or as part of the research study.

Interviewer--administered measures: The interviewer measures will be administered by the practicing clinician at initial clinical interviewer and by study staff blind to the treatment condition at pre-, mid-, and post-tx.

(1) The MINI-Kids (Sheehan et al., 2010). This is a clinician-administered, structured interview that is currently administered as part of the PADC standard evaluation. Administered at clinical interview only.

(2) Pediatric Anxiety Rating Scale (*PARS; (Group, 2002).* The PARS is an interviewer administered scale consisting of five items assessing anxiety severity, frequency, distress, avoidance, and interference. The PARS has good psychometric properties (Group, 2002) and has been used as the primary continuous outcome measure in previous treatment studies (e.g., (Walkup et al., 2008).

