The design of the current study is intended to maximize participation through providing options for participation. First, families have the option to provide data without submitting to randomization of treatment condition. The inclusion of families that are willing to complete the research assessments even though they are unwilling to be randomized to a comparison condition is intended to minimize the number of families that decline to participate. As such, this option increases the likelihood that participants accurately represent the population of patients seen in the PADC. Because these patients will receive PCET, it increases the number of patients receiving the intervention of most interest. In addition, because these families will participate in a baseline period of no treatment before attending the first treatment session, symptom improvement with treatment can be compared to that without treatment. Similarly, by allowing families to select the chance to be randomized to one or both CBT or PCET-5day as a comparator, we intend to maximize the number of patients for whom there is an acceptable option.

Personnel

Therapy will be provided by the staff of the PADC and psychology fellows that have completed the PADC rotation. The PI has trained and supervised all therapists and will provide additional training in the traditional CBT protocol. Assessments will be conducted by the study staff, blind to condition. The PI will provide training in the assessments.

Statistical Plan

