We anticipate that all patients will see minimal improvement in symptoms during the baseline period between the clinical evaluation and baseline pre-tx, and significant improvement from pret-tx to mid-tx and post-tx. In addition, we hypothesize that patients treated in the either PCET condition will demonstrate greater reductions in anxiety symptoms and impairment, as well as require fewer total treatment sessions, compared to patients in traditional CBT. To test this hypothesis, repeated-measures analyses of variance (which controls for baseline symptom severity) will be conducted to assess the change that occurs over time and between conditions. Because treatment changes after mid-treatment for some conditions, but not others, we will examine the changes at mid-treatment and post-treatment separately. The primary outcome variable will be change in symptom severity on a continuous variable as measured by the IE administered CGI-S. Secondary outcomes will be anxiety symptoms measured through parentreport (SCAS-P), child-report (SCAS-C), and clinician report (PARS). Dichotomous measures of improvement used in the literature will include receiving a score of 1 or 2 on the CGI-I, reduction on the PARS of 35% (response) and 50% (remission). Tertiary outcome variables will be impairment measured through the CSDS. Efficiency will be measured at the group level by number of treatment hours (included phone contacts) and symptom change effect size per hour of intervention. Number of dropouts vs. completers will be examined. Finally, we will examine treatment acceptability through the rate of drop-out and ratings of alliance. All statistical analyses will be conducted using intent-to-treat and completer analyses. Because patients that agree to each randomization option may differ in unmeasured ways, comparator analyses will be run in two ways. First, to avoid biasing the results by combining incompatible groups, we will include patients in comparisons only if they agreed to be randomized to each option (i.e., only patients that agreed to the possibility of being randomized to CBT will be included in the comparison between PCET-I and CBT). Second, to maximize power, we include all patients with randomization agreement as between subject variables. Exploratory analyses will include examining the relation to randomization choices and the moderating effects on outcome of diagnosis (OCD vs. anxiety disorder), symptom severity, age, medication use, etc.

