Power Statement: Based on the mean mid-tx CGI-S scores from the pilot study (PCET= 2.33, sd= .8; CBT = 3.17, sd =.8) and 14 patients are required per group to achieve 80% power to detect a difference between two groups at a p value of .05. Thus, the current proposed sample size of 20 participants be treatment conditions should be sufficient.

In regard to acceptability, we will assess the acceptability of each treatment to patients and their families. A between-groups analysis of variance will be conducted to assess for differences in the alliance and satisfaction of each treatment at posttreatment. Further, we will also conduct between-group mean comparisons of the number of drop outs.

Sample representativeness will be examined through group differences between patients that participated and those that declined through t-tests and chi-square analyses of symptom and demographic data collected at the clinical assessment.

Remuneration

Patients can earn up to \$50 for participation: up to \$25 for completing research assessments (\$5 for pre-treatment assessment and \$10 for each of the mid- and post-treatment assessments); up to \$25 for randomization: \$15 if they agree to the possibility of being randomized to one comparator and additional \$10 for agreeing to be randomized to the second comparator. All remuneration will be paid when the participant completes the study, and may be pro-rated based on completion of assessments. Patient remuneration will be payed from [name] research funds.

7. Possible Discomforts and Risks:

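### Planned size is given both as sixty randomised (20 per condition) and as 120 families (40 per condition), and the power statement does not say which families its 20 counts

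*Combined protocol and SAP*

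**What the plan says.** All of this is in the current text of the combined protocol and SAP.

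- **Section 3, Abstract:** "Sixty children and adolescents seeking treatment for anxiety in an outpatient pediatric anxiety clinic will be randomized" to individual PCET (PCET-I), traditional CBT or the group intensive (PCET-5day).
- **Section 6, Participants:** "A total of 120 families (240 participants) (40 in each treatment condition"). The section repeats the goal of 240 participants and expects to reach it in about twelve months.
- **Section 6, Statistical Plan, Power Statement:** from pilot mid-treatment CGI-S means of 2.33 (PCET) and 3.17 (CBT), SD .8 in each, it derives 14 per group for 80% power at .05 and ends: "Thus, the current proposed sample size of 20 participants be treatment conditions should be sufficient".

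Three further places bear on who is counted.

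- **Section 6, Procedures:** families choose what they will accept. "They will then be asked if they are willing to be randomized to a treatment from two or three of the options". For the rest, "Families that did not agree to randomization will be scheduled in PCET (individual or intensive group depending on preference").
- **Section 6, Design Justification**, on families who are not randomised: "Because these patients will receive PCET, it increases the number of patients receiving the intervention of most interest".
- **Section 6, Statistical Plan:** the comparator analyses are run in two ways. In the first, "only patients that agreed to the possibility of being randomized to CBT will be included in the comparison between PCET-I and CBT". The second takes in all patients, with agreement to randomisation entered as a between-patient factor. Neither is named as primary.

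**The concern.** The Abstract and the Power Statement agree with each other and differ twofold from the Participants section. Planned size is a figure that readers later use to judge whether a trial finished as intended. Here, stopping with 20 in CBT and stopping with 40 could each be described afterwards as meeting the plan.

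The second gap is separate. A count per condition is not the same as a count per comparison in this design. The PCET-I group can hold families who were never randomised, and families who accepted only PCET-5day as the comparator. Neither kind enters the first PCET-I versus CBT analysis. If the 20 counts everyone treated in a condition, the plan gives no number for that analysis.

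**Working it through.** **1. The plan's own 14 per group.** Inputs from the Power Statement: difference 3.17 − 2.33 = 0.84; SD 0.8; d = 0.84/0.8 = 1.05. Sidedness is not stated; two-sided is assumed.

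- Normal approximation: n = 2 × [SD × (1.960 + 0.842)/difference]² = 2 × (0.8 × 2.802/0.84)² = 14.24 per group, 15 when rounded up.
- Two-sample t-test: 15.26, so 16 when rounded up. Power at 14 is 76.2%.
- The SD is printed to one decimal. At SD 0.75, which prints as .8, d = 0.84/0.75 = 1.12 and 14 per group gives 81.4%.

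The 14 is therefore reproduced closely enough and is taken no further as an error.

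**2. The totals.** 3 × 20 = 60 matches the Abstract. 3 × 40 = 120 matches the Participants section. 120/60 = 2.

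**3. Can both be true?**

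- *Sixty randomised out of 120 enrolled.* Families outside randomisation go only to PCET, so the CBT arm is filled by randomisation alone. Forty in CBT is then 40 randomised to CBT, while the Power Statement has 20. Taking 40 of the sixty for CBT would leave 60 − 40 = 20 randomised families for both PCET conditions together, which also contradicts 20 per condition.
- *Children against children plus parents.* The Participants section counts 240/120 = 2 participants per family. Forty families are then 80 participants, and 20 participants would be 10 families. Neither matches.
- *Illustration, assuming equal allocation within each family's chosen options (no ratio is stated).* Let a families accept only CBT as comparator and b accept both comparators. Expected CBT = a/2 + b/3. Twenty in CBT needs 40 (b = 0) to 60 (a = 0) CBT-willing families; 40 needs 80 to 120. Sixty randomised families would be expected to give between 60/3 = 20 and 60/2 = 30 in CBT. The conflict does not depend on this assumption.

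**4. What each size delivers.** Two-sided t-test, alpha .05, d = 1.05, no dropout, n per arm within the comparison:

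| n per arm | Power | Difference detectable with 80% power (CGI-S points) |
|---|---|---|
| 15 | 79.3% | not computed |
| 16 | 82.0% | 0.82 |
| 20 | 89.9% | 0.909 × 0.8 = 0.73 |
| 40 | 99.6% | 0.634 × 0.8 = 0.51 |

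For SDs from 0.75 to 0.85, power at 20 per arm runs from 93.2% to 86.1%.

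**5. If the 20 or 40 counts families outside the comparison.** The documents give no share of families willing to be randomised to CBT, so these shares are assumptions, applied to both arms for simplicity:

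- 75% inside: 15 of 20 gives 79.3%; 30 of 40 gives 97.9%.
- 50% inside: 10 of 20 gives 60.3%; 20 of 40 gives 89.9%.

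The 80% floor of 16 per arm is 16/20 = 80% of the smaller count and 16/40 = 40% of the larger.

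**The case against.** The strongest reply is that nothing turns on this. Either per-arm figure exceeds what the plan's inputs require, so no conclusion changes and the defect is one of reporting. That stands, and it limits the severity. It does not remove the conflict, because the two sizes can detect different effects and only one can be the plan.

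Second, it would be too much to say that the documents set no enrolment goal. The Participants section states one twice and supports it with clinic flow: more than 350 evaluations a year, a third continuing, is about 350/3 = 117 families in twelve months, close to 120. That stands too. It shows that 120 was thought through. It does not show that 120 is the governing figure, because the Power Statement presents its 20 per condition as current.

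Third, the restriction to CBT-willing families applies to one of two analyses; the second uses everyone. This is correct, and so the undefined 20 affects the two analyses differently. It is also why the Power Statement has to say which analysis and which families it has in mind.

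A reader might also infer that the 14 per group is a miscalculation, since a two-sided t-test with SD .8 needs 16. The documents do not support that. The SD is rounded, the calculation method is not named, and the planned test is described as "repeated-measures analyses of variance (which controls for baseline symptom severity) will be conducted", which may need fewer patients than an unadjusted t-test.

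**Conclusion.** The planned size is stated in two incompatible ways, 60 and 120 in total or 20 and 40 per condition, and at least one place must be wrong. The readings that might reconcile them fail, chiefly because CBT can be filled only by randomisation. Separately, the Power Statement does not define the families it counts.

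It is tempting to conclude that the trial is underpowered. The documents do not show this. With d = 1.05, a two-sided t-test and no dropout, power is 89.9% at 20 per arm and 99.6% at 40, if those numbers are reached within the PCET-I versus CBT comparison. The condition matters because fewer than 16 per arm takes power below 80%, and the plan gives neither a willingness share nor a dropout allowance. The figures in step 5 of the working illustrate this and are not forecasts.

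Severity is moderate: a planning figure that needs correcting, with adequate power at either value.

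**What to change.** - Give one target in the Abstract, the Participants section and the Power Statement. The documents do not settle which figure is current, so the investigators must say.
- State whether that target counts randomised families or all enrolled families, and keep to families or children as the unit throughout.
- Restate power for the chosen target, naming the test and its sidedness.
- Give the number expected in PCET-I and in CBT among families who agreed to possible CBT, and list non-randomised families separately. Say which of the two comparator analyses the power figure refers to.

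The cost is wording in three places and one short recalculation. Neither the design nor enrolment has to change.

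### Representativeness is a question about the size of differences, but the plan answers it only with t-tests and chi-square tests, with no effect sizes, intervals or variable list

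*Combined protocol and SAP*

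**What the plan says.** The method is one sentence in section 6, Statistical Plan, after the power statement: participants and decliners will be compared "through t-tests and chi-square analyses of symptom and demographic data collected at the clinical assessment". The same check appears in two other places, neither of which adds a method.

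- The Abstract (section 3) describes a chart review of "patients that accept and those that decline participation in the treatment study".
- Section 6, Participants, sets the aim of establishing how far the sample reflects the clinic's patients, and describes a broader comparator: "the clinical assessment data will be compared to patients not enrolled in the study, but for whom Research Authorization is available".

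Section 6, Design Justification, presents representativeness as a benefit of letting families take part without randomization. That option "is intended to minimize the number of families that decline to participate" and so "increases the likelihood that participants accurately represent the population of patients seen in the PADC".

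For this check the plan gives no effect measure, confidence interval, significance level, multiplicity rule, list of variables or expected number of decliners.

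**The concern.** A test of no difference returns a p-value, which mixes the size of a difference with the number of patients. The stated aim concerns size alone. Two things follow.

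- With a small comparison group, a clinically noticeable difference can be non-significant, and the reader is not shown how large it might be.
- With many variables and no multiplicity rule, one or more significant results can be expected by chance even if participants and the others do not differ.

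What is at stake is the trial's statement about generalizability. The check as written cannot say how representative the sample is on any given measure, or how precisely that is known.

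**Working it through.** **The plan's own figure.** None is stated for this comparison. The only power figure, 14 per group, concerns PCET against CBT on mid-treatment CGI-S and has no bearing here.

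**Inputs from the document.**

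- Participants: "A total of 120 families (240 participants) (40 in each treatment condition" (section 6, Participants); the Abstract says sixty. Both are used.
- Flow: "The PADC typically evaluates more than 350 patients per year, approximately one-third of which continue into the treatment program", so 350/3 ≈ 117 families a year enter treatment.
- Duration: "we anticipate a recruitment period of approximately twelve months".
- Variables at Time 0 (Table 2): PARS, CGI-S, SCAS-P, SCAS-C, CSDS-P, CSDS-C, CAM-P and CAM-C (8), plus two Treatment Confidence forms. The Demographic Form names at least five items. That gives 8 + 5 = 13, or 15 with Treatment Confidence.

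**Assumptions.** Two-sided 0.05 for each test. The number of decliners is not given, so 10 to 40 is used for illustration. For the broader comparator, 350 − 120 = 230 (or 350 − 60 = 290), as if all had Research Authorization.

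**Step 1: dependence on group size.** Power comes from the noncentral t distribution with N + m − 2 degrees of freedom and noncentrality d·√(Nm/(N+m)), for N participants and m comparison patients. The 95% interval half-width is about t(0.975)·√(1/N + 1/m) SD.

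| N | m | Power, 0.3 SD | Power, 0.5 SD | Detectable at 80% | CI half-width |
|---|---|---|---|---|---|
| 120 | 10 | 15% | 33% | 0.93 SD | 0.65 SD |
| 120 | 20 | 23% | 54% | 0.68 SD | 0.48 SD |
| 120 | 30 | 31% | 68% | 0.58 SD | 0.40 SD |
| 120 | 40 | 37% | 78% | 0.51 SD | 0.36 SD |
| 120 | 230 | 76% | 99% | 0.32 SD | 0.22 SD |
| 60 | 20 | 21% | 48% | 0.73 SD | 0.51 SD |
| 60 | 290 | 56% | 94% | 0.40 SD | 0.28 SD |

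For a chi-square comparison of 50% with 30%, power is 37% at 120 v 20 and 96% at 120 v 230. The same true difference may thus be significant or not according to which comparator is used.

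**Step 2: chance findings.** If nothing differs and the tests are independent, P(at least one p < 0.05) = 1 − 0.95^k.

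- k = 13: 49%. k = 15: 54%.
- Equally correlated test statistics (simulated), correlation 0.3: 42% and 46%. Correlation 0.5: 33% and 36%.
- Expected false positives: 13 × 0.05 = 0.65 to 15 × 0.05 = 0.75.

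If only the four symptom scales (PARS, CGI-S, SCAS-P, SCAS-C) and five demographic items were tested, k = 9 gives 1 − 0.95^9 = 37% under independence and about 27% at correlation 0.5.

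**Step 3: what a difference means for representativeness.** Participants belong to the population they are meant to represent. Their mean minus the mean of participants plus decliners equals [m/(N+m)] × (participant mean − decliner mean). At the detectable differences for N = 120:

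- m = 20: 0.68 × 20/140 = 0.10 SD
- m = 30: 0.58 × 30/150 = 0.12 SD
- m = 40: 0.51 × 40/160 = 0.13 SD

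A large participant–decliner gap moves the sample only slightly from the group offered the study when decliners are few.

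**The case against.** The strongest objection is Step 3. If few families decline, the participants are nearly the whole group offered the study, and low power against decliners does little harm to representativeness within that group. This stands. A reader might infer from the Design Justification that the check is weakest exactly when recruitment succeeds. Power against decliners does fall as their number falls, but so does the weight that decliners carry, so that inference is not supported.

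The decliner count is also unknown. About 117 treatment entrants a year against 120 enrolled families in about a year would leave almost no decliners from that pool. Under the broader comparator in the Participants section, the power problem largely disappears for differences of 0.5 SD. This stands too: low power is conditional on the comparator, not a fixed property of the plan.

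A reader might further infer that a non-significant result will be reported as similarity, or that one significant result will be taken to refute representativeness. The plan says neither. It says only that group differences will be examined, and offers no other criterion.

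Finally, this is a descriptive side check, and parent, child and clinician ratings of the same child's anxiety are unlikely to be independent. Both points are fair. They limit the severity and explain why the chance-finding figure is a range.

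**Conclusion.** The point holds as a mismatch between question and method. The plan asks about degree and names only tests, which do not report size and whose results turn on an unstated number of comparison patients. Over 13 to 15 variables, the chance of at least one spurious significant result is about 33% to 54%, assuming 0.05 per test and correlations from 0.5 down to zero; a narrower variable list would lower it. The power figures rest on assumed comparator sizes and are illustrations, not predictions. Severity is low: neither the primary CGI-S comparison nor allocation is affected.

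**What to change.** In the Statistical Plan, replace the representativeness sentence with these elements:

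1. List the clinical-assessment variables to be compared and state the comparison group, reconciling the Abstract, Participants and Statistical Plan descriptions.
2. Report the numbers participating and declining, and the number of comparison patients with data on each variable.
3. For each variable, report the standardised difference (means or proportions) with its 95% confidence interval.
4. Report also the difference between participants and participants plus decliners, calculated as the decliner fraction times the participant–decliner difference.
5. Base the conclusion on the size and precision of these differences, not on p-values.

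A rule that declares similarity only when the whole interval lies within a tight bound is not advised. With 120 participants and 10 to 40 decliners the half-width is 0.65 to 0.36 SD, so a bound of ±0.25 SD, for example, could not be met even by an observed difference of zero. A Bonferroni correction is not the remedy either: 0.05/15 = 0.0033 per test would reduce power further and still not report size.

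The cost is a change of wording, using data already planned. The downside is that imprecise comparisons will be visible as such.
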